## 3. Planned Analyses

The following analyses will be performed for this study:

### 3.1. DATA AND SAFETY MONITORING BOARD (DSMB)

There will be at least 3 DSMB meetings for reviewing safety data in this study. Analysis for first and second DSMB meetings will be described in a separate DSMB SAP; while the third (all patients at week 26) and onward will be based on this SAP where analyses described in section 8-12 and 16 will be performed. Other analyses may be added in case they are thought to affect DSMB safety review, however no statistical inference will be included in order to avoid an inflation of the type I error.

The first DSMB analysis will be considered as Interim Analysis of 10 patients per group (30 patients in total) of safety data collected up to Week 4 whose safety report will be submitted to regulatory. For additional details on DSMB meetings, please refer to the DSMB charter dated 26Jan2017.

### 3.2. FINAL ANALYSIS (W52 CSR)

The analysis of primary, secondary and exploratory endpoints, including PK/PD, efficacy, safety and

---

Document:	\\eedc-vnasc01\Biosdata\Archigen\SAIT101\YWA21301\Biostatistics\Documentation\SAP		
Author:		Version Number:	V2.0
		Version Date:	13Feb2019

Template No: CS\_TP\_BS016 Revision 4  
Effective Date: 01Apr2016

Reference: CS\_WI\_BS005

immunogenicity, will be performed per protocol based on procedures outlined in this SAP based on the 52-week data of all patients.

The study will be unblinded only at Week 52 and a Week 52 CSR (W52 CSR) will be prepared based on the 52-week data of all patients.

The analysis for W52 CSR will be performed by IQVIA Biostatistics following sponsor authorization of this Statistical Analysis Plan, database lock and sponsor authorization of analysis sets.

### **3.3. EXPLORATORY ANALYSES**

The exploratory analyses will be described in following sections, for those analyses which are not described in this SAP will be performed as ad hoc analysis after unblinding, if needed. The subgroups to be used will be based on the results of analysis of PK, PD, efficacy, safety, immunogenicity and concomitant medication.

## **4. Analysis Sets and Protocol Deviations**

Analysis sets or exclusions therein will be determined through review of clinical database and protocol deviations prior to database lock and the unblinding of the study. A blinded data review meeting will be set up then to decide on the final allocation rules to assign subjects to the analysis sets.

Note that the PK/PD parameter analysis will be only performed after data base lock. A blinded data review meeting of PK/PD data will be done to decide the final allocation rules to assign subjects to the PK and PD analysis sets. The PK scientist will only be unblinded once the PK/PD parameter analysis has been finalized.

Analysis sets will be listed by subject.

### **4.1. ENROLLED SET [ENR]**

The Enrolled Set (ENR) consists of all subjects who provide informed consent for this study.

### **4.2. RANDOMIZED SET [RAN]**

The Randomized Set (RAN) consists of all screened subjects who receive a randomization number. For analyses and displays based on RAN, subjects were classified according to the treatment they are assigned at randomization.

### **4.3. FULL ANALYSIS SET [FAS]**

The Full Analysis Set (FAS) of the study consists of all RAN patients in accordance with the intended treatment arm, regardless of the treatment actually received. The FAS will be one of the populations used for the efficacy endpoints.

### **4.4. SAFETY ANALYSIS SET [SAF]**

The Safety Analysis Set (SAF) consists of all RAN patients who received at least one dose of study drug during Part A or Part B. Subjects will be analyzed according to the treatment received. The SAF is used as the basis for all safety analyses up to Week 52.

---

Document:	\\ieedc-vnasc01\Biosdata\Archigen\SAIT101\YWA21301\Biostatistics\Documentation\SAP	Version Number:	V2.0
Author:		Version Date:	13Feb2019

Template No: CS\_TP\_BS016 Revision 4  
Effective Date: 01Apr2016

Reference: CS\_WI\_BS005

If there is any doubt whether a subject was treated or not, they will be assumed treated for the purposes of analysis.

#### 4.5. PER PROTOCOL SET [PP]

The Per Protocol Set (PP) consists of all RAN patients who received at least both infusions of study drug in Part A and continued study assessments up to Week 24. Patients with any critical and/or major protocol deviations that affect the efficacy assessments will be assessed for inclusion in the set. Patients may be excluded from the PP set if they did not meet key eligibility criteria, were taking prohibited concomitant medication, received the wrong study drug, or other situations that may affect the efficacy assessments.

Protocol deviations or the situation that leads to exclusion from the PP will be specified and authorized prior to unblinding the treatment arms. Efficacy endpoints will also be summarized on the PP.

#### 4.6. PHARMACOKINETIC ANALYSIS SET [PKS]

The PK analysis set will include all patients who receive both planned doses of SAIT101 or MabThera® or Rituxan® in Part A (i.e., first course), have at least one estimable primary PK parameter value and have no major protocol deviations or events thought to significantly affect the PK of the drug.

Major protocol deviations or events thought to significantly affect the PK of the drug include (but not limited to) missing dose or incorrect dose, wrong study drug, drug infusion interrupted permanently, sampling date and time not available, sample processing errors that might render a subject's bioanalytical data to be inaccurate etc. Subjects with these issues will be reported in the study report.

Subjects in the PKS will be analyzed according to the treatment received.

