### **3.7.3 Individual Patient**

If a patient discontinues the study treatment prematurely, the reason given must be fully evaluated and recorded appropriately in the source documents and the patient's eCRF. If the patient is discontinued from study treatment because of an AE, that AE should be indicated as the reason for discontinuation.

The Investigator can discontinue treatment of a patient at any time if medically necessary. In addition, patients meeting the patient discontinuation criteria must be discontinued from the study treatment.

Patients will be discontinued from the study treatment in the following circumstances:

- A patient who does not meet the enrolment criteria is inadvertently randomized, that patient must be discontinued from study treatment and the Sponsor or Clinical Research Organization (CRO) must be contacted.
- The Investigator decides that the patient should be discontinued from study treatment. If this decision is made because of an intolerable AE or a clinically significant laboratory value, the study drug is to be discontinued and appropriate measures are to be taken. The Sponsor or designee is to be notified immediately.
- Patient non-compliance, defined as refusal or inability to adhere to the study schedule or procedures (see Section 3.12).
- Treatment with a prohibited concomitant medication other than the use of appropriate medications for the treatment of AEs under the direction of the Sponsor and/or Investigator or Sub-investigator
- Lack of efficacy. Subjects who lack efficacy can be included in the PK and efficacy analysis. Patients receiving rescue therapy prior to Week 24 would not be eligible for second course of infusion.
- Patients who meet any of the following specific safety discontinuation criteria, however can be included for the PK analysis:
  - Patients who develop severe infusion-related reactions, especially severe dyspnea, bronchospasm or hypoxia, should have the infusion interrupted immediately to receive aggressive symptomatic treatment. In all patients, the infusion should not be restarted on the same day until complete resolution of all symptoms. At this time, the infusion may be initially resumed at the discretion of the Investigator at not more than one-half the previous rate. If the same ADRs occur for a second time, the infusion should be permanently discontinued.
  - Active TB

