## **6.2.1 Analysis Sets**

### **6.2.1.1 Pharmacokinetic Analysis Set**

The PK analysis set will include all patients who receive both planned doses of SAIT101 or MabThera® or Rituxan®, have a measured drug serum concentration and have no major protocol deviations or violations thought to significantly affect the PK of the drug. Reasons for excluding patients from the PK Analysis set will be specified in the statistical analysis plan.

Major protocol deviations or violations thought to significantly affect the PK of the drug include (but not limited to) missing dose or incorrect dose, sampling date and time not available, sample processing errors that might render a subject's bioanalytical data to be inaccurate etc. Subjects with these issues will be reported in the study report.

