## 13. Pharmacokinetics Analysis

The PK data collected in Part A and Part B (up through Week 24) will be analyzed according to the treatment administered.

Serum concentrations of rituximab at the time points pre-defined in the study protocol will be measured by a validated method and used for the PK analysis.

Treatment of PK data affected by important protocol deviations and/or events will include the following:

- Randomized study drug not administered or not fully administered, or wrong trial drug administered: In case a dose is not administered or fully administered, any parameters for this subject, if calculated, for this dose and the subsequent dose will not be included in descriptive and/or inferential statistics; the subject will not be part of the PK analysis set per definition. In case of wrong trial drug being administered, patients will be analyzed and included according to the actual treatment they received (rather than the planned treatment), unless there are other additional factors or changes involved that would impact PK.
- Dose is administered outside of the time window provided in protocol (i.e., visit window of  $\pm 1$  day [i.e. 24 hours] for dose on Day 15): Due to the long half-life and extended duration of blood sampling collections, the impact of sampling time deviations on  $AUC_{(0-inf)}$ ,  $AUC_{(0-inf)}$ -related parameters, and  $AUC_{(0-last)}$  would be considered negligible and those parameters will generally not be excluded from descriptive and/or inferential statistics. Similarly,  $C_{max,d2}$  will not be excluded.
- Total duration of infusion not available (i.e., start and/or stop time of infusion missing): Any concentrations or PK parameters based fully or partially on the affected dose will be evaluated at the BDRM.
- Interruption of infusion: Due to the long half-life of the drug, interruptions are expected to have minimal impact on PK parameters that are susceptible to infusion interruptions, as long as the full dose is administered. No parameters will be excluded based on infusion interruptions.
- Pharmacokinetic samples at important phases of the PK disposition curve collected outside the protocol-defined window and/or missing: Important phases include time points around the end-of-infusion, the last sampling time point, and the trough concentration collected prior to dosing on Day 15.

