$AUC_{(0-\text{inf})}$	Area under the serum concentration-time curve from zero (immediately predose on Day 1) extrapolated to infinite time ( $\mu\text{g}\cdot\text{h}/\text{mL}$ ), calculated by linear up/log down trapezoidal summation and extrapolated to infinity by addition of the last quantifiable concentration divided by the elimination rate constant: $AUC_{(0-\text{last})} + C_{\text{last}}/\lambda_z$ . For presenting data purpose, symbol $AUC_{(0-\text{inf})}$ instead of $AUC_{(0-\infty)}$ will be used in all PK analysis and reporting.
$AUC_{(0-d15)}$	Area under the serum concentration-time curve from zero (immediately predose on Day 1) until Day 15 prior to infusion ( $\mu\text{g}\cdot\text{h}/\text{mL}$ ), calculated by linear up/log down trapezoidal summation.  Actual time/concentration on Day 15 will be used for the calculation of this parameter unless the parameter is derived by interpolation (see below); 

• A window of 312 to 360 hours postdose for the 336-hour (Day 15) time point (which has been selected as a window that would not create an influence of more than <math>\pm 5\%</math> on the AUC) will be used as an acceptance criterion, for calculation using actual time/concentration on Day 15, and for inclusion of this parameter in descriptive and inferential statistics;

• If the 336-hour sample was collected after 360 hours (i.e., outside the defined time window) but prior to the second dose, then a log-linear interpolation will be used to derive the concentration at 336 hours for computation of <math>AUC_{(0-d15)}</math>;

• If the 336-hour sample is missing or was collected before 312 hours, the <math>AUC_{(0-d15)}</math> will be set to missing.

$AUC_{(w2-w24)}$	Area under the serum concentration-time curve from Week 2 (predose) to Week 24 ( $\mu\text{g}\cdot\text{h}/\text{mL}$ ), calculated by linear up/log down trapezoidal summation.
$AUC_{(0-w12)}$	Area under the serum concentration-time curve from zero (predose) to Week 12 ( $\mu\text{g}\cdot\text{h}/\text{mL}$ ), calculated by linear up/log down trapezoidal summation.

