$C_{\text{trough}}$	Trough (predose) concentration ( $\mu\text{g}/\text{mL}$ ) prior to second infusion on Day 15, obtained directly from the observed concentration versus time data. 

• If the sample was collected outside of a window of 312 to 360 hours postdose, <math>C_{\text{trough}}</math> will be excluded for descriptive and inferential statistics.

$C_{\text{max,dose1}}$	Maximum serum concentration ( $\mu\text{g}/\text{mL}$ ) over the 1 st dosing interval, obtained directly from the observed concentration versus time data. This parameter will only be reported if the end-of-infusion concentration is available and evaluable.
$C_{\text{max,dose2}}$	Maximum serum concentration ( $\mu\text{g}/\text{mL}$ ) over the 2 nd dosing interval, obtained directly from the observed concentration versus time data. This parameter will only be reported if the end-of-infusion concentration is available and evaluable.

---

Document:	\\ieedc-vnasc01\Biosdata\Archigen\SAIT101\YWA21301\Biostatistics\Documentation\SAP	Version Number:	V2.0
Author:		Version Date:	13Feb2019

Template No: CS\_TP\_BS016 Revision 4  
Effective Date: 01Apr2016

Reference: CS\_WI\_BS005

$t_{\max, \text{dose1}}$	Time of maximum concentration (h) post-infusion over the 1 st dosing interval, obtained directly from the observed concentration versus time data.
$t_{\max, \text{dose2}}$	Time of maximum concentration (h) post-infusion over the 2 nd dosing interval, obtained directly from the observed concentration versus time data.
$\lambda_z$	Apparent terminal rate constant (1/h), determined by linear regression of the terminal points of the log-linear concentration-time curve. Visual assessment will be used to identify the terminal linear phase of the concentration-time profile. A minimum of 3 data points will be used for determination.
$t_{1/2}$	Apparent terminal half-life (h), determined as $\ln 2/\lambda_z$ .
CL	Systemic clearance after intravenous dosing (L/h), calculated as dose (1 st + 2 nd dose) divided by $AUC_{(0-\text{inf})}$ .
$V_D$	Volume of distribution following intravenous dosing (L), calculated as dose (1 st + 2 nd dose) divided by $[\lambda_z \cdot AUC_{(0-\text{inf})}]$

The following PK parameters will be calculated for diagnostic purposes and listed, but will not be summarized.

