$t_{1/2}$ , Interval	The time interval (h) of the log-linear regression to determine $\lambda_z$ .
$t_{1/2}$ , N	Number of data points included in the log-linear regression analysis to determine $\lambda_z$ . A minimum of 3 data points will be used for determination.
$R_{sq}$	Goodness-of-fit statistic for calculation of $\lambda_z$ (Regression coefficient).
%AUC ex	Percentage of $AUC_{(0-\text{inf})}$ obtained by extrapolation, calculated as $[(C_{\text{last}}/\lambda_z)/AUC_{(0-\text{inf})} \times 100]$ .

The following criteria will be assessed:

- if  $AUC_{(0-t)}$  is less than 80.0% of  $AUC_{(0-\infty)}$  (i.e. %AUCex>20.0%), the data will be flagged in the listing.
- if predose concentration is greater than 5% of  $C_{\max, \text{dose1}}$  for a subject, the concentration data and parameters for this subject will be flagged in the listing and excluded from summary statistics.

For partial areas from interval time 1 ( $t_1$ ) to time 2 ( $t_2$ ), if  $t_2$  is missing,  $AUC_{(t_1-t_2)}$  will not be calculated.

Pharmacokinetic parameters will be listed and summarized by treatment using descriptive statistics (n, mean, SD, CV%, minimum, median, maximum, geometric mean, and geometric CV%, except that  $t_{\max}$  will be reported with n, minimum, median, and maximum only).

The additional following summaries of PK parameters will be generated:

- By treatment and region (US, EU, Other)
- By treatment and age category (18-60 years and >60 years)
- By treatment and sex
- By treatment and ADA status at baseline.

The PK parameters,  $AUC_{(0-t)}$ ,  $AUC_{(0-\text{inf})}$ ,  $AUC_{(0-d15)}$ ,  $C_{\max, \text{dose2}}$  after the second infusion on Day 15, and  $C_{\text{trough}}$ , before the second infusion on Day 15 will be considered the co-primary PK endpoints. All other PK endpoints will be regarded as secondary.

A statistical comparison of the loge-transformed primary parameters between treatments will be based on an analysis of variance model. No covariates will be included. The difference in least squares means between the

Document: \\ieedc-vnasc01\Biosdata\Archigen\SAIT101\YWA21301\Biostatistics\Documentation\SAP	
Author:	Version Number: V2.0
	Version Date: 13Feb2019

Template No: CS_TP_BS016 Revision 4	Reference: CS_WI_BS005
Effective Date: 01Apr2016	

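### One PK set requiring both infusions drops first-dose-only patients from AUC(0-d15) and Ctrough, which are complete before the second infusion, and no planned analysis restores them

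*SAP*

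**What the plan says.** **The set.** Protocol 6.2.1.1 opens its definition with "The PK analysis set will include all patients who receive both planned doses of SAIT101" (or a comparator). SAP 4.6 repeats this and ties it to the first course: "The PK analysis set will include all patients who receive both planned doses of SAIT101 or MabThera® or Rituxan® in Part A". It also lists a missing dose and a permanently interrupted infusion among the events that exclude a patient. SAP 13 says of a patient with a dose not given or not fully given that "the subject will not be part of the PK analysis set per definition".

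**The endpoints.** All five co-primary parameters are analysed on this set. Two of them end before the second infusion. AUC(0-d15) runs from predose on Day 1 "until Day 15 prior to infusion". Ctrough is the concentration "prior to second infusion on Day 15, obtained directly from the observed concentration versus time data".

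**Patients who stop.** Protocol 3.7.3 has the heading item "Patients who meet any of the following specific safety discontinuation criteria, however can be included for the PK analysis". The bullets under it include permanent stopping of an infusion after a repeated reaction. A delay of more than 15 days to the second infusion comes further down; whether it belongs to the same list depends on the indentation. Protocol 3.4.4 admits withdrawn patients to the PK analysis only if they meet the PK set. Protocol 3.6.6 keeps patients who stop treatment in the visit schedule to Week 52, with drug level among the things to be measured.

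**The concern.** Whether the second infusion is given cannot change the value of AUC(0-d15) or Ctrough, yet it decides whether that value is analysed. Under protocol 3.2.2, an infection or other adverse event after Day 1 delays the second infusion, and a delay of more than 15 days ends treatment. So the selection acts on an event after randomization and first dosing, and that event could depend on product or exposure. A comparison restricted in this way is no longer fully protected by randomization.

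Two endpoints times three pairs makes 6 of the 15 equivalence tests. Protocol 6.3 requires all three pairs to pass on every primary endpoint, so each of the six counts.

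The additional PK analyses in SAP 13.2 add covariates, look at baseline ADA status, or address site 10703. None includes first-dose-only patients, so the plan would not show whether the restriction mattered.

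**Working it through.** **1. The texts side by side.** Take a patient who completes the Day 1 infusion, has an evaluable Day 15 sample, and then stops for a safety reason without a second infusion.

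- Protocol 3.7.3: may be included for PK.
- Protocol 3.4.4, if the patient also withdraws from the study: only if the PK set is met.
- Protocol 6.2.1.1 and SAP 4.6: not in the set.
- SAP 13: the sentence first removes parameters "for this dose and the subsequent dose will not be included in descriptive and/or inferential statistics". For a missed second dose, that alone would leave the first-dose parameters. It then removes the whole patient.
- SAP 13 and 13.2 on sampling deviations: exclusion is by parameter. A Day 15 sample outside 312 to 360 hours removes Ctrough but generally leaves AUC(0-inf).

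**2. Planned numbers (SAP 2.3).** 84 / (1 − 0.10) = 93.3, rounded up to 94 per group. This reproduces the plan's figure.

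**3. Power per test.** Inputs from SAP 2.3 and 13.2: ratio 1.000, limits 0.80 to 1.25, one-sided 5%, CV 33.0% (range 26.3% to 37.3%), 84 per group. Method: two one-sided t-tests with log SD = sqrt(ln(1 + CV²)) and SE = SD × sqrt(2/n). The documents give no rate of missed second infusions, so I take the whole 10% withdrawal as the upper bound, 94 − 84 = 10 per group.

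| CV | n = 84 | n = 94 | Gain |
|---|---|---|---|
| 33.0% | 99.5% | 99.8% | 0.3 points |
| 37.3% | 98.1% | 99.0% | 0.9 points |

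The n = 84 column is close to the plan's stated 98% to 99.0% per test.

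**4. Selection effect.** Let qT and qR be the shares of patients with a complete first infusion who are excluded in the two arms. Let r be the ratio of their geometric mean exposure to that of patients given both infusions, assumed equal in both arms. The log mean over all such patients in an arm is the both-infusions mean plus q × ln r. The test-to-reference ratio in the both-infusions set therefore differs from the ratio in everyone by the factor exp((qT − qR) × |ln r|), or the reciprocal if the reference arm loses more. All q and r below are assumptions.

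| Shares excluded in the two arms | r = 0.9 | r = 0.7 |
|---|---|---|
| 2% and 2% | 1.000 | 1.000 |
| 2% and 5% | 1.003 | 1.011 |
| 2% and 8% | 1.006 | 1.022 |
| 0% and 10% | 1.011 | 1.036 |

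Worked for the last cell: exp(0.10 × 0.357) = 1.036.

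**5. Scale.** The 90% CI at 84 per group spans the ratio divided and multiplied by exp(1.654 × SE). That factor is 1.085 at CV 33% and 1.096 at CV 37.3%. In the extreme cell, with a true ratio of 1, the chance of passing one test at n = 84 is 98.3% (CV 33%) or 95.5% (CV 37.3%), against 99.5% and 98.1% without the shift.

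**The case against.** A reader might infer that the SAP contradicts protocol 3.7.3. The documents do not support that. The rule requiring both doses is the protocol's own in 6.2.1.1, so the SAP follows the protocol. Section 3.7.3 is permissive, and several of its criteria (malignancy, pregnancy, hepatitis B reactivation) can arise long after both Part A infusions; those patients can satisfy both sections. Section 3.4.4 also makes entry conditional on the set. What remains is narrower: a patient stopped before the second infusion is allowed in by one section and can never qualify under another.

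A reader might also infer that SAP 13 would keep first-dose parameters and is overridden from elsewhere. The same sentence removes the patient, so SAP 13 and 4.6 reach the same result.

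There are safeguards. SAP 4 settles the PK set at a blinded review with the PK scientist still blinded, SAP 4.6 has affected patients reported, and SAP 4.8.1 keeps excluded data in the listings. The exclusions are therefore visible and not driven by results. That stands, but blinding the decision does not undo selection on a post-dose event.

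The 10% allowance already covers the lost numbers, and nothing in the documents shows that patients who completed the first infusion but missed the second had lower exposure. Both points stand and limit the size of the concern.

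Finally, protocol 5.4.5 says that severe reactions typically occur during the first infusion. Patients who never complete it stay excluded under the change proposed here, so part of any product-related loss remains.

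**Conclusion.** The concern holds as a limited point about selection and consistency. For AUC(0-d15) and Ctrough the requirement of a second infusion has no pharmacokinetic basis, conditions on a post-randomization event, and is not examined by any sensitivity analysis. The documents also leave an unresolved tension between protocol 3.7.3 and protocol 6.2.1.1 with 3.4.4, which the SAP settles by exclusion without comment.

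Its likely effect is small. The shift is zero if rates and exposure deficits match across arms. It is about 0.3% to 3.6% under imbalances from 2% against 5% up to 0% against 10%, with exposure 10% to 30% lower in the excluded patients. These inputs are assumptions, and the direction is unknown. Such a shift would change a conclusion only where a confidence limit already lay close to 0.80 or 1.25. Patients whose second infusion was late but given are not removed by this rule.

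**What to change.** - For AUC(0-d15) and Ctrough, define evaluability by parameter: first infusion complete, and an evaluable Day 15 sample (predose, or the scheduled sample in patients not redosed) within 312 to 360 hours. At minimum, prespecify this as a supportive analysis beside the current set.
- Keep the both-infusions rule for AUC(0-t), AUC(0-inf) and Cmax,dose2.
- In SAP 13, say that only the dose 1 end-of-infusion samples bear on AUC(0-d15), and in 13.2 say whether interpolation for samples after 360 hours applies to patients never redosed.
- Reconcile protocol 3.7.3 and 6.2.1.1 with SAP 4.6 and 13, and record the change in SAP 2.6.

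**Cost.** No new data collection, since drug levels are already scheduled after treatment stops. N will differ by endpoint, as it already does under the sample rules. If the primary analysis changes, it is a stated departure from protocol 6.2.1.1 and more than a wording edit to the SAP; the supportive analysis avoids that. Patients whose first infusion was not completed remain excluded, and the report should give their number by arm.
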